27.1.1 Deaths

All deaths including those that occurred on-treatment and post-treatment, will be listed (SAF), post treatment deaths will be flagged. In addition to the on-treatment deaths and additional summary of all deaths (on-treatment + post-treatment) will be provided.

28.1.1 General rules for reporting

10.7.3.1.1 AE tables

- i. All safety analyses will be done using the Safety Set (SAF). The incidence of treatment-emergent AEs will be summarised in incidence tables.
- ii. AEs will be summarised by SOC and PT using the Medical Dictionary for Regulatory Activities (MedDRA) version 21.0 and will be updated to the most current version at the end of the trial. The SOCs and PTs will be used for tabulation.
- iii. AE frequency tables will display the number of events (incidence), number of patients experiencing an event and the percentage of patients with the event by System Organ Class (SOC) and Preferred Term (PT).
- iv. If a patient experiences more than one occurrence of the same AE, the occurrence with the greatest severity and the closest association with the study drug will be counted in the summary tables.
- v. If a patient reported more than one AE with the same preferred term, the AE with the maximum toxicity grade will be presented.
- vi. If a patient reported more than one AE within the same primary system organ class, the patient will be counted only once with the maximum toxicity grade at the system organ class level, where applicable.
- vii. The most common AEs reported ($\geq 10\%$ for each preferred term) will be presented in descending frequency according to its incidence starting from the most common event.

10.7.3.1.2 AE listings

- i. All AEs will be listed by patient, along with information regarding onset, duration, relationship to study drugs, intensity, toxicity grade, action taken with study drug, treatment of event, and outcomes. This listing will be generated for all patients in the SAF.
- ii. In the AE listings, AEs that started prior to the administration of any study drug will be flagged as pre-treatment AEs. AEs that start 30 days after the last study treatment and which are not related to one of the study drugs will be flagged as post-treatment AEs.
- iii. Special AE listings displaying details of the event(s) captured on the eCRF in a compact format will be provided for:
 - Serious Adverse Events.
 - TEAEs of toxicity grade 3 or grade 4.
 - AEs leading to discontinuation of treatment (split by MOR00208, LEN and overall).
 - TEAEs of special interest.
 - TEAEs suspected to be related to study drug

-
- Treatment-emergent SAEs
 - TEAEs pertaining to the SOC '*infections and infestations*'
 - AEs leading to death.
 - Pre-treatment adverse events (i.e., adverse events that happened before administration of any study drug). This listing will be generated for all patients successfully screened but never treated. The pre-treatment AEs will be determined using the analysis population of 'All screened patients'.

29.1.1 AE summaries

10.7.3.1.3 TEAEs (serious and non-serious)

The following summaries will be provided:

- i. All TEAEs regardless of study treatment relationship by primary SOC, PT, grade.
- ii. All TEAEs regardless of study treatment relationship by primary SOC, PT, intensity.
- iii. Most frequent TEAEs (*at least in 10% of the patients*), regardless of study treatment relationship by SOC, PT and grade.
- iv. TEAEs regardless of study treatment relationship \geq grade 3 by primary SOC, PT and grade.
- v. TEAEs regardless of study treatment relationship of grade 3 or grade 4 by primary SOC, PT and grade.
- vi. TEAEs suspected to be related to the study drug by primary SOC, PT, and grade (according to NCI-CTC toxicity criteria) (split by MOR00208, LEN, both drugs at the same time, and any study drug).
- vii. TEAEs suspected to be related to the study drug by primary SOC, PT, and intensity (according to NCI-CTC toxicity criteria) (split by MOR00208, LEN, both drugs at the same time, and any study drug).
- viii. TEAEs suspected to be related to the study drug of \geq grade 3 by primary SOC, PT and grade (split by MOR00208, LEN, both drugs at the same time, and any study drug).
- ix. TEAEs suspected to be related to the study drug of grade 3 or grade 4 by primary SOC, PT and grade (split by MOR00208, LEN, both drugs at the same time, and any study drug).
- x. Most frequent TEAEs suspected to be related to the study drug (*at least in 10% of the patients*) by primary SOC, PT and grade (split by MOR00208, LEN, both drugs at the same time, and any study drug).
- xi. TEAEs leading to any action on MOR00208, on LEN, or either on MOR00208 *or* on LEN regardless of study treatment relationship, by primary SOC, PT and grade.
Note: Any Action = Dose reduction/Dose interruption/Permanent discontinuation.

-
- xii. TEAEs leading to discontinuation of treatment (split by MOR00208, LEN, both drugs at the same time, and overall) regardless of study treatment relationship by primary SOC, PT and grade.
 - xiii. Most frequent Non-serious TEAEs, regardless of study treatment relationship by primary SOC, PT and grade (at least 5% incidence).

10.7.3.1.4 Treatment-emergent SAEs

The following summaries on treatment-emergent SAEs will be produced:

- i. Treatment-emergent SAEs regardless of study treatment relationship, by primary SOC, PT, grade.
- ii. Most frequent treatment-emergent SAEs (*at least in 2% of the patients*), regardless of study treatment relationship, PT and grade.
- iii. Treatment-emergent SAEs regardless of study treatment relationship \geq grade 3 by primary SOC, PT, and grade.
- iv. Treatment-emergent SAEs of grade 3 or grade 4 regardless of study treatment relationship by primary SOC, PT, and grade.
- v. Treatment-emergent SAEs suspected to be related to the study drug by primary SOC, PT, grade (split by MOR00208, LEN, both drugs at the same time, and any study drug).
- vi. Treatment-emergent SAEs suspected to be related to study drug \geq grade 3 by primary SOC, PT, and grade (split by MOR00208, LEN, both drugs at the same time, and any study drug).
- vii. Treatment-emergent SAEs suspected to be related to the study drug of grade 3 or grade 4 by primary SOC, PT, and grade (split by MOR00208, LEN, both drugs at the same time, and any study drug).
- viii. Most frequent treatment-emergent SAEs suspected to be related to the study drug (*at least in 2% of the patients*) by SOC, PT and grade (split by MOR00208, LEN, both drugs at the same time, and any study drug).
- ix. Treatment-emergent SAEs of grade 5 by primary SOC and PT.

10.7.3.1.5 AESIs

AEs of special interest will be presented by primary SOC, PT and grade.

10.7.3.1.6 Deaths

Deaths will be summarized as follows:

STATISTICAL ANALYSIS PLAN

 MorphoSys AG
 MOR208C203

-
- Treatment-emergent deaths (deaths observed within 30 days after last administration of study treatment) in total and grouped by:
 - Deaths *related* to disease progression as indicated on the eCRF pages for ‘End of Survival Follow-up’ or ‘End of Treatment’: all reasons/causes for death containing the phrases:
 - ‘PROGRESSIVE DISEASE’
 - ‘PROGRESSION DISEASE’
 - ‘PROGRESSION OF DISEASE’
 - ‘LYMPHOMA’
 - ‘MULTIPLE RELAPSING AND REFRACTORY DLBCL’
 - ‘DLBCL DISEASE PROGRESSION’
 - ‘LYMPHOMA’
 - ‘DISEASE PROGRESSION’
 - ‘PROGRESSIVE DESEASE’
 - ‘PROGRESSION DESEASE’
 - ‘RELAPSE’
 - ‘IMMEDIATE CAUSE OF DEATH: PARALYTIC ILEUS, DUE TO ABDOMINAL LYMPHOMA PROGRESS’
 - ‘PROGRESSIVE DISEASE’
 - ‘PD’
 - ‘RECURRENCE OF LARGE CELL LYMPHOMA’
 will be considered as related to disease progression.
 - Deaths *unrelated* to disease progression: All on-treatment deaths not considered as related to disease progression will be considered as unrelated to disease progression.

 - Post-treatment deaths (deaths observed after 30 days after last administration of study treatment) overall and grouped by:
 - Deaths related to disease progression as indicated on the eCRF page for ‘End of Survival Follow-up’: all reasons for death containing the phrases:
 - ‘PROGRESSIVE DISEASE’
 - ‘PROGRESSION DISEASE’
 - ‘PROGRESSION OF DISEASE’
 - ‘LYMPHOMA’
 - ‘MULTIPLE RELAPSING AND REFRACTORY DLBCL’
 - ‘DLBCL DISEASE PROGRESSION’
 - ‘DISEASE PROGRESSION’
 - ‘PROGRESSIVE DESEASE’

-
- 'PROGRESSION DESEASE'
 - 'RELAPSE'
 - 'IMMEDIATE CAUSE OF DEATH: PARALYTIC ILEUS, DUE TO ABDOMINAL LYMPHOMA PROGRESS'
 - 'PROGRESIVE DISEASE'
 - 'PD'
 - 'RECURRENCE OF LARGE CELL LYMPHOMA'

will be considered as related to disease progression.

- Deaths unrelated to disease progression: all post-treatment deaths not considered as related to disease progression will be considered as unrelated to disease progression.
- Total number of deaths (All deaths (on-treatment + post treatment) are included) overall and grouped by:
 - Deaths related to disease progression as indicated on the eCRF pages for 'End of Survival Follow-up' or 'End of Treatment': all reasons/causes for death containing the phrases:
 - 'PROGRESSIVE DISEASE'
 - 'PROGRESSION DISEASE'
 - 'PROGRESSION OF DISEASE'
 - 'LYMPHOMA'
 - 'MULTIPLE RELAPSING AND REFRACTORY DLBCL'
 - 'DLBCL DISEASE PROGRESSION'
 - 'DISEASE PROGRESSION'
 - 'PROGRESSIVE DESEASE'
 - 'PROGRESSION DESEASE'
 - 'RELAPSE'
 - 'IMMEDIATE CAUSE OF DEATH: PARALYTIC ILEUS, DUE TO ABDOMINAL LYMPHOMA PROGRESS'
 - 'PROGRESIVE DISEASE'
 - 'PD'
 - 'RECURRENCE OF LARGE CELL LYMPHOMA'

will be considered as related to disease progression.

- Deaths unrelated to disease progression: All deaths not considered as related to disease progression will be considered as unrelated to disease progression.

A listing on the deaths based on the 'all patients screened' population will be produced indicating if a death is PD-related, and if the death happened on treatment, pre-treatment, or post-treatment.

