6.7 Prior and Concomitant Therapy

Administration and Recording of Prior and Concomitant Therapy – General Instructions

Any prior, concomitant, or procedural medications or therapy given to or taken by the patient within 1 month prior to commencement of the study (30 days prior to signing the ICF) and up to the End of Treatment Visit (EOT) must be recorded in the source documents and the eCRF along with the indication, route and dosage. Such medications (including over-the-counter medications) must be listed on the concomitant medications form in the eCRF. Starting from the EOT Visit, only anticancer treatments and, in case of an AE, other relevant concomitant medications (at the discretion of the investigator) should be entered. The investigator should instruct the patient not to take any additional medications (including over-the-counter--products) during the study without prior consultation.

For patients who will be administered MOR208 despite progression of disease / relapse, an **Unscheduled Visit** including all procedures described for EOT Visit need to be performed in order to capture the event (i.e. disease progression/relapse) for the antibody treatment to continue further.

At the EOT visit (or at the Unscheduled Visit after disease progression / relapse) as described in the above paragraph), any antineoplastic therapy after end of study drug treatment must be recorded as well.

Patients may receive concomitant medications that are medically indicated as standard care for the treatment of symptoms, AEs, and intercurrent illnesses. Medications to treat concomitant diseases like diabetes, hypertension, bronchial asthma, chronic obstructive pulmonary disease (COPD) etc., are allowed. Patients will also receive therapy to mitigate side effects of the study medication as clinically indicated, as well as best supportive care (BSC) as per institutional guidelines. This may include, but is not limited to, antiemetics, antidiarrhoeals, anticholinergics, antispasmodics, antipyretics, antihistamines, analgesics, antibiotics, and other medications intended to treat symptoms.

Recording of Prior Lines of Anti-lymphoma Therapy

Information should be provided on any previous DLBCL-specific- therapies since the time point of the first diagnosis of DLBCL. The generic or the trade name may be recorded.

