17.6 Deaths

Section 10.7.3.1.6 describes how deaths will be summarized according to the following categories: PD-related vs. non-PD-related. The list of terms determining that a death is PD-related will be extended by the terms “Progression”, “Study disease” and “Progression of the disease”. The following terms will lead to a classification into the new “Unknown” category in terms of PD-relatedness:

- “End stage marrow failure”
- “Unkown”

In case that for a patient more than one cause of death is reported in different sections of the eCRF, the patients’s death will be categorized as PD-related if at least one of the causes of death is classified as PD-related.

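### The text search that labels deaths as progression-related also catches causes such as 'COPD exacerbation' and 'Progression of cardiac failure', and so can understate deaths unrelated to progression

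*SAP*

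**What the plan says.** SAP 10.7.3.1.6 (Deaths) divides treatment-emergent, post-treatment and all deaths into those related and those unrelated to disease progression. Related deaths are "all reasons/causes for death containing the phrases" on a fixed list. The list holds long phrases, misspellings and one whole sentence, but also the short strings 'PD', 'RELAPSE' and 'LYMPHOMA'.

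For treatment-emergent and total deaths the text comes from the End of Survival Follow-up or End of Treatment page. For post-treatment deaths only the former is named ("Deaths related to disease progression as indicated on the eCRF page for" End of Survival Follow-up). The remainder is defined by default: "All deaths not considered as related to disease progression will be considered as unrelated to disease progression".

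Addendum 2.0, SAP 17.6, changes this in three ways:

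- "The list of terms determining that a death is PD-related will be extended by the terms" 'Progression', 'Study disease' and 'Progression of the disease'.
- Two terms go to a new 'Unknown' category.
- Where several causes are recorded, the death "will be categorized as PD-related if at least one of the causes of death is classified as PD-related".

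The available text gives no word boundary, no exclusion terms and no medical review of the assigned category. Letter case is addressed for the first-line treatment search in SAP 20.10, but not for deaths.

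**The concern.** A search for text that contains 'PD' also finds it inside 'COPD', and a search for 'Progression' finds the progression of anything. Concomitant COPD is foreseeable in this population. Protocol 6.7 says that medications for concomitant diseases including "chronic obstructive pulmonary disease (COPD) etc., are allowed", and it provides for COPD exacerbations during treatment. That passage concerns permitted medication, not eligibility, but it shows that the condition and its abbreviation are expected in the records.

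At stake is the split between progression and other causes in the death summaries and listing. In a single-arm trial there is no comparator against which to judge deaths not due to the lymphoma, so their count should not depend on an accident of spelling. Each false match of this kind moves a death out of the unrelated group.

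**Working it through.** There is no stated figure to reproduce, because the question is what the rule does to text. The inputs are the 14 distinct phrases of SAP 10.7.3.1.6 and the 3 terms added by SAP 17.6. They were applied to test causes in three ways: contained anywhere (the rule as written), whole word, and exact text. The test causes were written for this check; they are not trial data. The table ignores case.

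| Test cause | 10.7.3.1.6 list, contained | With 17.6, contained | With 17.6, whole word | With 17.6, exact |
|---|---|---|---|---|
| COPD EXACERBATION | 'PD' | 'PD' | none | none |
| Progression of cardiac failure | none | 'Progression' | 'Progression' | none |
| PNEUMONIA, LYMPHOMA IN REMISSION | 'LYMPHOMA' | 'LYMPHOMA' | 'LYMPHOMA' | none |
| CHRONIC OBSTRUCTIVE PULMONARY DISEASE | none | none | none | none |
| PROGRESSION OF LYMPHOMA (a true case) | 'LYMPHOMA' | 'LYMPHOMA', 'Progression' | both | none |

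Four things follow.

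1. The 'COPD' match arises from 10.7.3.1.6 alone, and it occurs whether or not case is ignored. COPD written out in full does not match, so the abbreviation decides the category.
2. The cardiac failure match arises only through 17.6. If case is respected, it occurs when the word is typed 'Progression' but not 'PROGRESSION'.
3. A word boundary alone removes the first false match but not the second or third. Exact matching removes all three but misses the true case in the last row.
4. The default category errs the other way. A cause recorded as 'REFRACTORY DLBCL' contains none of the 17 strings and would be called unrelated. The listed phrase that ends in those words is longer.

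**Size.** If U deaths are truly unrelated and k of them are falsely matched, the table shows U − k, an understatement of k/U. Neither number is in the documents. Purely as an assumption, U = 10 with k = 1 to 2 gives 10% to 20%, and U = 4 with k = 1 gives 25%. These figures show only that small counts are sensitive.

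**Reach.**

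- PFS counts death from any cause (SAP 10.2.2), and progression there needs objective evidence (SAP 6.14.2).
- OS counts death from any cause (SAP 10.4.2).
- Neither endpoint uses the search.

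**The case against.** **The latest rule may differ.** The SAP contents list Section 21.2 on PD-related and other deaths (Addendum 6.0), but its text was not available for review. The change log describes added terms and an algorithm adapted to new entries, which reads as an extension, not tighter matching. That cannot be confirmed, so this objection stands as a limit on confidence.

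**Someone evidently reads the entries.** The misspellings and the full sentence suggest a list built from recorded causes, and 17.6 sends particular terms to 'Unknown'. This makes an unnoticed error less likely. But no step in the available text uses the deaths listing to correct a category.

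**Stronger readings that a reader might infer, and why they fail:**

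- *That such deaths would disappear from the safety report.* They would not while on treatment. Protocol 8.2 requires on-study deaths not attributed to progression to be recorded as adverse events. The SAP tabulates grade 5 serious events (10.7.3.1.4, 10.7.3.1.7) and lists adverse events leading to death (10.7.3.1.2), without the string search. This protection is weaker later. More than 30 days after the last dose only related adverse events are recorded, while survival follow-up runs for up to 5 years (Protocol 7.2.5).
- *That TTP is biased.* SAP 10.5.2 counts deaths due to lymphoma and censors others, but does not say that this search identifies them.
- *That the net error runs one way.* The false matches do, but unlisted progression wording errs in the opposite direction. The net direction is not established.
- *That deaths have been misclassified.* The documents show no recorded cause that triggers a false match.

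**Conclusion.** Wrong as written, minor. On a literal reading of 10.7.3.1.6 with 17.6, causes that have nothing to do with the lymphoma are classed as progression-related because they contain 'PD' or 'Progression'. Naming the lymphoma as being in remission has the same effect. This can understate unrelated deaths in the death summaries and listing. It matters most for post-treatment deaths, because an unrelated late death would normally not appear in the adverse event tables.

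The conclusion rests on two assumptions: that containing means a match anywhere in the text, and that Section 21.2 does not already tighten the matching. Any effect on TTP depends on a link that the SAP does not state.

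**What to change.** In SAP 10.7.3.1.6 and 17.6:

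- Match 'PD' only as a whole word.
- Count 'Progression' or 'Relapse' only when it stands alone or refers to lymphoma, DLBCL or the study disease. A looser test that the text mentions a disease is not enough, since it would still admit progression of cardiac disease.
- Do not count 'Lymphoma' when the text states remission.
- State how letter case is handled.
- Before database lock, compare each assigned category with the verbatim cause, using the deaths listing planned in 10.7.3.1.6 and the survival follow-up listing planned in 10.4.3. Show the End of Treatment cause where that page is the source. Check both directions: false matches, and progression deaths left in the unrelated group.

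Apply the same to Section 21.2 if it does not already do so.

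The cost is an edited search expression and one read-through of listings that are already planned. The count of unrelated deaths may change slightly.

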10.7.3.1.7 Overall Summary of AEs

In addition, an **Overall AE summary table** will be presented showing the incidence and number of patients with at least one of the events:

- At least one TEAE.
- At least one treatment-emergent SAE.
- On-treatment deaths.
- Post-treatment deaths.
- At least one treatment-emergent SAE suspected to be related to the study drug (split by MOR00208, LEN, MOR00208 and LEN, and any study drug).
- At least one TEAE suspected to be related to the study drug (split by MOR00208, LEN, MOR00208 and LEN, and any study drug).
- At least one drug-related TEAE with grade 3 or grade 4 (split by MOR00208, LEN, MOR00208 and LEN, and overall).
- At least one drug-related TEAE by intensity (split by MOR00208, LEN, MOR00208 and LEN, and overall).
- At least one AESI.
- At least one TEAE leading to any action on MOR00208, on LEN, on MOR00208 and LEN, or on any study drug
- TEAEs leading to discontinuation of treatment (split by MOR00208, LEN, MOR00208 and LEN, and overall).
- Treatment-emergent SAEs of grade 5.
- At least one TEAE of PT 'Infusion-related reactions (IRRs)' \geq grade 3

Additional safety-related analyses on vital signs, physical examinations, electrocardiogram, and laboratory data are being described in Section 13.

10.8 Secondary objective 8

10.8.1 Objective

To assess the potential immunogenicity of MOR00208 (anti-MOR00208 antibodies).

10.8.2 Endpoint: Percentage of patients who develop anti-MOR00208 antibodies as determined by a positive anti-MOR00208 antibody titre.

10.8.3 Analysis

Assessment of immunogenicity will be performed using the immunogenicity analysis population (IAS).

1. The results of the anti-MOR00208 antibody assessment will be listed for each anti-MOR00208 sample analysed, including a categorization if the anti-MOR00208 antibody response is neutralizing or non-neutralizing.

Note: For 2. and 3. below, “negative” is defined as a sample reported negative in the screening assay OR confirmatory assay. “Positive” is defined as a sample being reported positive in the confirmatory assay.

2. The absolute number and percentage of the following categories will be tabulated by visit:

Patient has positive anti-MOR00208 antibodies (yes/no/missing) by visit:

- Yes, if a titre is available.
- No, if result is reported as negative.
- Missing, if anti-MOR00208 measurement is not available.

3. In addition, the absolute number and percentage of patients who develop anti-MOR00208 antibodies will be tabulated using the following categories:

Patient has developed positive anti-MOR00208 antibodies during study (yes/no/not evaluable/missing):

- Yes, if the patient has at least one positive post-baseline sample containing positive anti-MOR00208 antibodies, baseline sample has to be tested negative.
- No, if baseline as well as all post-baseline results are negative.
- Not evaluable, if the baseline sample of the respective patient was tested positive.
- Missing, if no post-baseline anti-MOR00208 measurement is available.

4. Results (n, mean, median, StD, minimum, maximum) of semi-quantitative anti MOR00208 antibody titre determinations of confirmed positive sample assessments will be tabulated by visit.

10.9 Secondary objective 9

